7.2.1 Safety Analyses

As this is a retrospective analysis, it is expected all adverse events will already have been reported at the time it was reported and thus safety analyses are not applicable for this study.

7.2.2 Summary of all Analyses

Outcome	Analysis Set	Supports Protocol Objective Number	Subgroup	Statistical Method	Strata	Missing Data
Baseline Characteristics	All patients	1	None	Descriptive Stats	None	Missing data will be summarized in table. Missing days from dates will be handled as per section 6 of this document.
Treatment patterns	- All patients who have received Palbociclib combination treatment.	1	Pre-menopausal patients ^a	Descriptive stats, Bar charts, Sankey Diagram	None	Missing data will be summarized in table and excluded from figures. Missing days from dates will be handled as per section 6 of this document.
Treatment patterns and sequencing pre and post CDK	- All patients	2	-Pre-CDK subgroup	Descriptive stats,	None	Missing data will be summarized in table. Missing

PFIZER CONFIDENTIAL

			-Post-CDK subgroup	Bar charts,		days from dates will be handled as per section 6 of this document.
Treatment duration (TTNT1/TTNT2)	- All patients	Exploratory	Premenop ausal patients ^a	KM Curve	Systemic therapies	Missing data will be excluded. Missing days from dates will be handled as per section 6 of this document.
Time to chemotherapy (TTC)	- All patients	Exploratory	Premenop ausal patients ^a	KM Curve	Systemic therapies	Missing data will be excluded. Missing days from dates will be handled as per section 6 of this document.
Overall Survival	- All patients	Exploratory	Premenop ausal patients ^a	KM Curve	Systemic therapies	Missing data will be excluded. Missing days from dates will be handled as per section 6 of this document.
Impact of COVID-19	- All patients	Exploratory	- Patients diagnosed one year before and within first year of the pandemic	Descriptive Stats, KM Curve, Bar charts, Sankey Diagram	None	Missing data will be excluded. Missing days from dates will be handled as per section 6 of this document.

^a Patients who are potentially pre-menopausal are included in this subgroup. Please refer to section 4.4 of this document for further details about how this group is defined.

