9.7. Data analysis

Detailed methodology for summary and statistical analyses of data collected in this study will be documented in a statistical analysis plan (SAP), which will be dated, filed and maintained by the sponsor. The SAP may modify the plans outlined in the protocol; any major modifications of primary endpoint definitions or their analyses would be reflected in a protocol amendment. Statistical analyses will be performed by PPD. The data will be analyzed using R (version and packages will be detailed in final SAP).

Descriptive analyses will be performed to summarize patients' baseline characteristics and outcomes of interest across the study cohort. Continuous variables will be described by the number of patients with valid/non-missing observations using mean, standard deviation (SD), minimum, maximum and quantiles (Q1, median, Q3). Categorical variables will be described by frequencies and related percentages. Number of missing observations will be reported for all variables. Time to event will be described using unadjusted Kaplan-Meier chart that will visually estimate the distribution of times to some events (i.e. progression), and will take into account those patients for which the event has not as yet occurred. Numbers at risk, cumulative incidence and survival medians will be reported for each curve. Endpoint definitions and how patients are censored for each endpoint will be further described in the SAP. Visualizations may be used to further describe treatment patterns, patient journeys, and other outcomes of interests if appropriate. The above planned data analyses are descriptive in nature and all subject to modification based on sample size and final data specifications. No inferential statistical analyses will be conducted.

PFIZER CONFIDENTIAL

Missing data will be excluded on a case by case basis and will not be imputed. This will mean that each table will not necessarily be based on the same number of patients.

CCI

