1 AMENDMENTS FROM PREVIOUS VERSION(S)

Amendment number	Date	SAP section(s) changed	Summary of amendment(s)	Reason
Version 2.0	2023-02-16	Title page	Change of protocol version identifier from "version 1.0" to "version 2.0" and the date from "2021-11-22" to "2023-01-24" and the author from PPD	SAP information has been updated. Change of staff at PPD
Version 2.0	2023-02-16	2.2 STUDY OBJECTIVES and 5.1 EFFICACY AND ENDPOINT(S) and 7.2 STATISTICAL ANALYSES	Change of "Secondary objective" with the deletion of "To evaluate efficacy of current treatment for Canadian breast cancer patients using surrogates for time to next treatment in the real-world setting including: 
• The length of treatment for the first line (TTNT1), the length of treatment for the second line (TTNT2), the time from cyclin-dependent kinase 4 and 6 (CDK4/6) inhibitor to starting chemotherapy (TTC) and overall survival (OS)• The length of treatment for short term versus long term responders" which is now included with the exact similar wording to the CCI section, except for the following wording "...the time from cyclin-dependent kinase 4 and 6 (CDK4/6) inhibitor to starting chemotherapy (TTC)..." which was replaced by "...the time from the date of ABC/MBC diagnosis to starting chemotherapy (TTC)..." in addition.	The secondary objective was adapted as the initial planned sample size (e.g., 180 patients) will be dramatically lower than expected (less than 30% of initial sample size); consequently, CCI As per clinical expert insight, the definition of TTC was clarified to the time from the date of ABC/MBC diagnosis to starting chemotherapy

PFIZER CONFIDENTIAL

Amendment number	Date	SAP section(s) changed	Summary of amendment(s)	Reason
			
“...last known activity” was replaced by “date of last follow-up or death”
 
These updates have been made throughout the document.
	

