6 HANDLING OF MISSING VALUES

For categorical variables, the number of missing responses will be shown as a separate category in the analysis. For continuous variables, the number of non-missing observations will be presented. Limited use of imputation methods will be used for missing dates. For instance, if the month and year are present for a date, then “15” would be input as the date to create a complete observation. Excluding dates, no other imputation methods will be used for missing or incomplete data.

PFIZER CONFIDENTIAL

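### Excluding missing data from the TTNT, TTC and OS curves selects on the outcome when an event is known but has no usable date

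*SAP*

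**What the plan says.** The summary table in SAP 7.2.2 gives the same missing-data entry for treatment duration (TTNT1/TTNT2), time to chemotherapy (TTC) and overall survival (OS): "Missing data will be excluded. Missing days from dates will be handled as per section 6 of this document". The baseline and treatment-pattern rows of that table say that missing data will be summarized; these three rows do not.

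SAP 6, to which the entry refers, opens with "Limited use of imputation methods will be used for missing dates". Its one worked case inserts day 15 "if the month and year are present for a date". It then closes the door on everything else: "Excluding dates, no other imputation methods will be used for missing or incomplete data".

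Protocol 9.7 is stricter: "Missing data will be excluded on a case by case basis and will not be imputed". It adds that the number of patients may differ from table to table, and Protocol 9.9 repeats that no imputation is planned. For the Kaplan-Meier curves, Protocol 9.7 says the estimate "will take into account those patients for which the event has not as yet occurred", and it defers the detail: "Endpoint definitions and how patients are censored for each endpoint will be further described in the SAP".

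In the public SAP, the endpoint list (5.1) and most of the time-to-event text and table in 7.2 are blacked out. Appendix A1.2 shows only a heading. The nearest visible wording on end dates is a phrase in the amendment table, "date of last follow-up or death".

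**The concern.** A date of death, or of starting chemotherapy or the next line, can be unknown only in a patient who is known to have had that event. A patient without the event needs no event date. If patients are excluded because the event date is unusable, membership of the analysis set depends on the outcome, and the curve loses events without losing the matching event-free patients. OS, TTC and TTNT then look longer than they are.

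The route to such records is plausible, though the documents do not describe it. The visible source for deaths and treatments is one hospital's health records, with no linkage mentioned, so an event that took place elsewhere could be noted without a month or year. The 3-year OS landmark is where the effect would be read.

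The planned reporting would not necessarily show it. Protocol 9.7 promises a count of missing observations for every variable, but a blank date of death can mean alive or undated, and a raw count does not separate the two.

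**Working it through.** The plan states no event count, missing-date rate or survival assumption for this cohort, so there is no figure to reproduce. The check is of direction and size.

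**Inputs**
- Low survival value: 22% at 5 years for stage IV (Protocol 7). At constant hazard, 3-year OS = 0.22^(36/60) = 0.403.
- High survival value: 95.6% at 12 months for palbociclib + AI in the cited Canadian chart review (Protocol 7). At constant hazard, 3-year OS = 0.956^3 = 0.874.
- Diagnosis from 01 January 2016 to 01 July 2021 and data cut-off 01 October 2021 (SAP 2.1 and 4.1): potential follow-up of 3 to 69 months.
- Expected size: less than 30% of 180 (SAP 1), so N is below 0.30 × 180 = 54.
- Share of deaths without a usable date, m: 5%, 10%, 20%. This is an assumption.

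**Only undated deaths excluded**

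Without censoring before 3 years, S' = S / [S + (1 − S)(1 − m)]. For S = 0.403 and m = 10%: 0.403 / (0.403 + 0.597 × 0.90) = 0.429. With censoring, Kaplan-Meier was run on 400,000 simulated patients (exponential survival, follow-up uniform on 3 to 69 months).

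| m | True 40.3%: formula | True 40.3%: Kaplan-Meier | True 87.4%: formula | True 87.4%: Kaplan-Meier |
|---|---|---|---|---|
| 5% | 41.6% | 41.4% (+1.1) | 87.9% | 87.9% (+0.6) |
| 10% | 42.9% | 42.6% (+2.2) | 88.5% | 88.5% (+1.1) |
| 20% | 45.8% | 45.2% (+4.9) | 89.6% | 89.7% (+2.3) |

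At a true 40.3%, the median moves from 27.4 months to 29.1 (m = 10%) or 31.3 (m = 20%).

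**Event-free patients excluded as well**

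| Patients excluded | True 40.3% | True 87.4% |
|---|---|---|
| Equal shares of events and censored, 5% to 30% | 40.3–40.4% | 87.3–87.5% |
| 10% of events, 20% of censored | 38.0% | 86.1% |
| 10% of censored only | 38.2% | 86.2% |

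The bias vanishes in the first row and reverses in the other two. In the extreme case where every event-free patient is dropped, as could happen for TTNT if each blank stop date were read as missing, a true 3-year value of 40.3% falls to 11.7%.

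**Censoring undated deaths instead**

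Censoring these deaths at a last contact just before death gives 44.1% (m = 10%) and 48.5% (m = 20%) against a true 40.3%. That is worse than exclusion.

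**Scale in this cohort**

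With 54 patients, the two survival values imply about 7 to 30 deaths by the cut-off, so 10% undated is about 1 to 3 patients. The standard error of 3-year OS without censoring is at least √(0.403 × 0.597 / 54) = 6.7 points at the low survival value.

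**The case against.** A reader might infer that the rule removes events only and therefore makes outcomes look better overall. The documents do not support that. The entry covers all missing data. The date of last follow-up is a separate extracted variable and can be missing in a patient without the event; the line of therapy or the systemic-therapy stratum can be missing in anyone. TTNT1 and TTNT2 are defined as length of treatment, so a blank stop date may mean that treatment continues, and excluding it would remove long durations. The net direction depends on relative missingness, which the documents do not give. This stands, and limits the point to the undated-event component.

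A reader might also infer that the sponsor has no rule for undated events. That cannot be asserted. The missing-value cells of the time-to-event table in SAP 7.2 are redacted and may hold one. SAP 6 offers day 15 only as an example and permits other limited date imputation. Protocol 9.7 lets the SAP modify its plans, so its ban on imputation is not decisive. The word excluded does not say whether the patient or the value is dropped, although the protocol's remark about changing denominators favours the patient. What remains is that SAP 7.2.2 and SAP 6 can both be read, and neither contains such a rule.

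On importance, the rows are labelled exploratory, all analyses are descriptive, and sampling error in fewer than 54 patients exceeds the bias computed for up to 20% undated deaths. That also stands. It lowers the priority but does not excuse a rule that selects on the outcome, since bias of this kind does not average out and each patient is about 2% or more of the cohort.

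**Conclusion.** The point holds for patients with a known event and no usable month or year. In the visible text they are excluded, that exclusion depends on the outcome, and taken alone it biases OS, TTC and TTNT towards longer times. For 3-year OS the overstatement is about 1 to 5 points at a true 40.3% and about 0.6 to 2.3 points at a true 87.4%. These sizes rest on an assumed 5% to 20% of deaths being undated, constant hazards, uniform entry, and survival figures from other populations. TTC and TTNT were not sized.

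The net direction of the whole exclusion rule is unknown. Because the result can go either way with who is dropped, the plan needs to separate a date that is blank because nothing happened from one that is unknown. This is a worthwhile correction to exploratory analyses and does not touch the primary objective on treatment patterns.

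**What to change.** If the redacted text already holds a rule for undated events, SAP 7.2.2 should point to it. Otherwise, replace the missing-data entry in the TTNT, TTC and OS rows with wording to this effect:

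- A patient known to have had the event, but without a usable date, is kept as an event. The date is bounded by the last record without the event and the first record reporting it, no later than 01 October 2021. The midpoint is used, and both bounds are shown as sensitivity results.
- A blank event or stop date with no record of the event means not occurred. The patient is censored at last follow-up and is not treated as missing.
- The numbers of patients with an approximated date and of patients excluded are reported under each curve, by event status.

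Reconcile the no-imputation statements in Protocol 9.7 and 9.9 with the date imputation in SAP 6.

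The cost is wording in both documents and two sensitivity curves for each endpoint affected. The bounding dates should come from the same notes already being extracted. The downside is that a few event dates are approximate.

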8 LIST OF TABLES AND TABLE SHELLS

PLEASE NOTE: The below tables and proposed analyses reflect the complete list of desired variables and analyses to be included in the study. However, inclusion of variables and type of analyses conducted will be dependent on availability of data from source documents and are subject to modification based on sample size and final data specifications.

Table 1: Demographics and Baseline characteristics of all patients and premenopausal patients.

Variables	Overall (N=) ^a	Premenopausal Patients (N=) ^b
Age		
N		
Mean (SD)		
Median		
Q1, Q3		
Minimum-Maximum		
Sex		
Female		
Male		
Unknown		
ECOG		
0		
1		
2		
3		
4		
Unknown		
Organ level metastatic site		
Bone		
Brain		
Lungs		
Liver		
Number of metastatic sites		
0		
1		
2		
3		
4		
Comorbidities		
Atrial fibrillation		
Hypertension		

PFIZER CONFIDENTIAL

Coronary Artery Disease/Myocardial infarction/Angina		
Diabetes Mellitus		
Stroke		
Tumour stage at diagnosis		
I		
II		
III		
IV		
Unknown		
Tumour grade		
1		
2		
3		
Unknown		
Tumour histology		
Lobular Carcinoma		
Ductal carcinoma		
Mixed		
DCIS		
LCIS		
Other		
Unknown		
ER Receptor status		
Positive		
Negative		
Unknown		
PR Receptor status		
Positive		
Negative		
Unknown		

^a Includes all study patients

^b Includes all study patients who are potentially in pre-menopause. Please refer to section 4.4 of this document for further details about how this group is defined.

Table 2: Demographics and Baseline characteristics of all Palbociclib treated patients and Palbociclib treated premenopausal patients.

Variables	Palbociclib treated patients (N=) ^a	Premenopausal Patients (N=) ^b
-----------	---	---

PFIZER CONFIDENTIAL

Age	N Mean (SD) Median Q1,Q3 Minimum-Maximum		
Sex	Female Male Unknown		
ECOG	0 1 2 3 4 Unknown		
Organ level metastatic site	Bone Brain Lungs Liver		
Number of metastatic sites	0 1 2 3 4		
Comorbidities	Atrial fibrillation Hypertension Coronary Artery Disease/Myocardial infarction/Angina Diabetes Mellitus Stroke		
Tumour stage at diagnosis	I II III IV Unknown		
Tumour grade	1		

PFIZER CONFIDENTIAL

2		
3		
Unknown		
Tumour histology		
Lobular Carcinoma		
Ductal carcinoma		
Mixed		
DCIS		
LCIS		
Other		
Unknown		
ER Receptor status		
Positive		
Negative		
Unknown		
PR Receptor status		
Positive		
Negative		
Unknown		

^a Includes patients who received Palbociclib treatment

^b Includes patients who received Palbociclib treatment and who are potentially in pre-menopause. Please refer to section 4.4 of this document for further details about how this group is defined.

Table 3: Demographics and Baseline characteristics stratified by type of responder

Variables	Short term responders (n=) ^a	Long term responders (n=) ^b
Age		
N Mean (SD) Median Q1,Q3 Minimum-Maximum		
Sex		

PFIZER CONFIDENTIAL

Female		
Male		
Unknown		
ECOG		
0		
1		
2		
3		
4		
Unknown		
Organ level metastatic site		
Bone		
Brain		
Lungs		
Liver		
Number of metastatic sites		
0		
1		
2		
3		
4		
Comorbidities		
Atrial fibrillation		
Hypertension		
Coronary Artery		
Disease/ Myocardial infarction /Angina		
Diabetes Mellitus		
Stroke		
Tumour stage at diagnosis		
I		
II		
III		
IV		
Unknown		
Tumour grade		
1		
2		
3		
Unknown		
Tumour histology		
Lobular Carcinoma		
Ductal carcinoma		
Mixed		

PFIZER CONFIDENTIAL

DCIS		
LCIS		
Other		
Unknown		
ER Receptor status		
Positive		
Negative		
Unknown		
PR Receptor status		
Positive		
Negative		
Unknown		

^a Defined as those who are on first line therapy for up to 3-6 months

^b Defined as those who are on first line therapy for more than 6 months

Table 4: Demographics and Baseline characteristics stratified by pre and post CDK subgroups

Variables	Pre-CDK ^a (N=)	Post CDK ^b (N=)
Age		
N		
Mean (SD)		
Median		
Q1, Q3		
Minimum-Maximum		
Sex		
Female		
Male		
Unknown		
ECOG		
0		
1		
2		
3		
4		
Unknown		
Organ level metastatic site		
Bone		
Brain		
Lungs		
Liver		
Number of metastatic sites		
0		
1		

PFIZER CONFIDENTIAL

	2		
	3		
	4		
Comorbidities			
	Atrial fibrillation		
	Hypertension		
	Coronary Artery		
	Disease/Myocardial infarction/Angina		
	Diabetes Mellitus		
	Stroke		
Tumour stage at diagnosis			
	I		
	II		
	III		
	IV		
	Unknown		
Tumour grade			
	1		
	2		
	3		
	Unknown		
Tumour histology			
	Lobular Carcinoma		
	Ductal carcinoma		
	Mixed		
	DCIS		
	LCIS		
	Other		
	Unknown		
ER Receptor status			
	Positive		
	Negative		
	Unknown		
PR Receptor status			
	Positive		
	Negative		
	Unknown		

^a Defined as treatment started between January 2016-May 2016

^b Defined as treatment started between January 2019- May 2019

Table 5: Demographics and Baseline characteristics stratified by time of diagnosis.

Variables	Before COVID-19 ^a (N=)	During COVID-19 ^b (N=)
-----------	-----------------------------------	-----------------------------------

PFIZER CONFIDENTIAL

Age	N Mean (SD) Median Q1, Q3 Minimum-Maximum		
Sex	Female Male Unknown		
ECOG	0 1 2 3 4 Unknown		
Organ level metastatic site	Bone Brain Lungs Liver		
Number of metastatic sites	0 1 2 3 4		
Comorbidities	Atrial fibrillation Hypertension Coronary Artery Disease/Myocardial infarction/Angina Diabetes Mellitus Stroke		
Tumour stage at diagnosis	I II III IV Unknown		
Tumour grade	1		

PFIZER CONFIDENTIAL

2		
3		
Unknown		
Tumour histology		
Lobular Carcinoma		
Ductal carcinoma		
Mixed		
DCIS		
LCIS		
Other		
Unknown		
ER Receptor status		
Positive		
Negative		
Unknown		
PR Receptor status		
Positive		
Negative		
Unknown		

^a Defined as patients who were diagnosed between March 10, 2019 – March 10, 2020.

^b Defined as patients who were diagnosed between March 11, 2020-March 11, 2021.

Treatment patterns and changes:

Table 6: Line 1 Treatment Patterns in patients who received Palbociclib

Variables	Overall (N=) ^a	Pre-menopausal patients (N=) ^b
Chemotherapy N, Mean Tx duration (SD)		
Chemo drug 1, n (%)		
Chemo drug 2, n (%)		
...		
Targeted therapy N, Mean Tx duration (SD)		
Targeted drug 1, n (%)		
Targeted drug 2, n (%)		
...		
...(Any other Class of therapy observed)		

^a Includes all patients who received Palbociclib

^b Includes patients who received Palbociclib and who are potentially in pre-menopause. Please refer to section 4.4 of this document for further details about how this group is defined.

Treatment patterns and changes in patients who received Palbociclib:

[figure not shown]

Figure 1: Classes of treatments over time in patients who received Palbociclib. Similar plots will be created for all lines of therapy. Stacked bar charts can be either absolute values (as shown) or percentages, as required.

Figure 2: Sankey Diagram of treatment of patients who received Palbociclib

Treatment patterns and changes in patients who received Palbociclib who are potentially in pre-menopause.

[figure not shown]
Figure 3: Classes of treatments over time in patients who received Palbociclib who are potentially in pre-menopause. Please refer to Figure 1 for reference as to how bar charts will look. Similar plots will be created for all lines of therapy.

GER CONFIDENTIAL

Figure 4: Sankey Diagram of treatment of patients who received Palbociclib who are potentially in pre-menopause

PFIZER CONFIDENTIAL

Pre and Post-CDK treatment patterns:

Table 7: Pre and post-CDK treatment patterns and sequencing in patients

	Pre-CDK ^a			Post-CDK ^b		
	Line 1	Line 2	Line 3	Line 1	Line 2	Line 3
Chemotherapy N, Mean Tx duration (SD)						
Chemo type 1, n (%)						
Chemo type 2, n (%)						
...						
Targeted therapy N, Mean Tx duration (SD)						
Targeted type 1, n (%)						
Targeted type 2, n (%)						
...						
...						

^a Defined as treatment started between January 2016-May 2016^b Defined as treatment started between January 2019- May 2019

Table 8: Sequencing of therapies after CDK 4/6 inhibitor

[figure not shown]
	Overall (N=)
Post-CDK received in L1	
Medicinal product name 1, n (%)	
Medicinal product name 2, n (%)	
...	
Post-CDK received in L2	
Medicinal product name 1, n (%)	
Medicinal product name 2, n (%)	
...	
Post-CDK received in L3	
Medicinal product name 1, n (%)	
Medicinal product name 2, n (%)	
...	

Bar charts

Figure 5: Classes of treatments over time in all patients. Please refer to Figure.1 for reference as to how bar charts will look. Similar plots will be created for all lines of therapy.

PFIZER CONFIDENTIAL

Time to event analyses in all patients:

Figure 6: TTNT1 in all patients by type of treatment

Figure 7: TTNT2 in all patients by type of treatment

Figure 8: TTC in all patients by type of treatment

Figure 9: Overall Survival in all patients by type of treatment

Table 9: Length of Line 1 treatment in short term vs long term responders

Variables	Short term responders (n=) ^a	Long term responders (n=) ^b
Chemotherapy N, Mean Tx duration (SD)		
Chemo type 1		
N		
Mean (SD)		
Median		
Q1,Q3		
Minimum-Maximum		
Chemo type 2		
N		
Mean (SD)		
Median		
Q1,Q3		
Minimum-Maximum		
...		
Targeted therapy N, Mean Tx duration (SD)		
Targeted type 1		
N		
Mean (SD)		
Median		
Q1,Q3		
Minimum-Maximum		
Targeted type 2		
N		
Mean (SD)		
Median		
Q1,Q3		
Minimum-Maximum		
...		

^a Defined as those who are on first line therapy for up to 3 to 6 months

^b Defined as those who are on first line therapy for more than 6 months

Time to event analyses in pre-menopausal patients:

Figure 10: TTNT1 in patients who are potentially in pre-menopause by type of treatment

Figure 11: TTNT2 in patients who are potentially in pre-menopause by type of treatment

Figure 12: TTC in patients who are potentially in pre-menopause by type of treatment

Figure 13: Overall Survival in patients who are potentially in pre-menopause by type of treatment

Table 10: Length of Line 1 treatment in short term vs long term responders in pre-menopausal patients^a

Variables	Short term responders (n=) ^b	Long term responders (n=) ^c
Chemotherapy N, Mean Tx duration (SD)		
Chemo type 1		
N		
Mean (SD)		
Median		
Q1,Q3		
Minimum-Maximum		
Chemo type 2		
N		
Mean (SD)		
Median		
Q1,Q3		
Minimum-Maximum		
...		
Targeted therapy N, Mean Tx duration (SD)		
Targeted type 1		
N		
Mean (SD)		
Median		
Q1,Q3		
Minimum-Maximum		
Targeted type 2		
N		
Mean (SD)		
Median		
Q1,Q3		
Minimum-Maximum		
...		
...		

^a Includes patients who are potentially in pre-menopause. Please refer to section 4.4 of this document for further details about how this group is defined.

^b Defined as those who are on first line therapy for up to 3 to 6 months

^c Defined as those who are on first line therapy more than 6 months

Impact of COVID-19:Treatment patterns in patients who were diagnosed before and during COVID-19:

Table 11: Treatment patterns in patients diagnosed before and during COVID-19.

	Before COVID-19 ^a	During COVID-19 ^b
Total visits from treatment, n		
Total visits from surgeries, n		
Total visits from radiation, n		
Total number of ABC/MBC diagnoses, n		
Average duration between date of diagnosis and line 1 treatment initiation.		
	N	
	Mean (SD)	
	Median	
	Q1, Q3	
	Minimum-Maximum	
Class and type of therapy initiated for Line 1 treatment.		
Chemotherapy N, Mean Tx duration (SD)		
Chemo type 1, n (%)		
Chemo type 2, n (%)		
...		
Targeted therapy N, Mean Tx duration (SD)		
Targeted type 1, n (%)		
Targeted type 2, n (%)		
...		
...		

[figure not shown]
^a Defined as patients who were diagnosed between March 10, 2019 – March 10, 2020.^b Defined as patients who were diagnosed between March 11, 2020-March 11, 2021.

Figure 14: Number of MBC diagnoses over time (example graph).

Bar charts

Figure 15: Classes of treatments in all patients who were diagnosed 1 year before and 1 year during COVID-19. Please refer to Figure.1 for reference as to how bar charts will look. Similar plots will be created for all lines of therapy.

KM Curve

Numbers at risk
Cum events

Figure 16: TTNT1 in patients who were diagnosed 1 year before and 1 year during COVID-19.

KM Curve

Numbers at risk
Cum events

Figure 17: Overall survival in patients who were diagnosed 1 year before and 1 year during COVID-19.

Treatment patterns in patients who were treated before and during COVID-19:

PFIZER CONFIDENTIAL

[figure not shown]

Table 12: Treatment patterns before and during COVID-19

	Before COVID-19 ^a			During COVID-19 ^b		
